9.3 Expectedness Classification of Adverse Events

An AE will be classified as either expected or unexpected (see Figure 6).

For the purpose of this study, expected AEs will be divided into non-captured and captured AEs. These distinctions were made based on the frequency of occurrence, severity of event, and risk to subject. All captured AEs will be documented in the eCRF.

Figure 6 Expectedness Classification of Adverse Events

Abbreviations: AE = adverse event; eCRF = electronic Case Report Form.

9.3.1 Expected Adverse Events

9.3.1.1 Captured Expected Adverse Events

The following expected AEs may occur at any time in the course of managing diabetes. Immediate or short term risks to subjects from some of these expected AEs are higher than those identified under Non-Captured Expected AEs.

Therefore, for the purposes of this study, the following expected AEs will be considered captured expected AEs and the AE Form in the eCRF needs to be completed:

- Symptomatic hypoglycemia episodes (see Section 9.2.2).
- Hyperglycemia in combination with medical intervention..
- Ketosis and ketoacidosis.

These captured expected AEs will be handled as follows:

Subjects will be instructed to follow their personal physicians' instructions for management of low and high blood glucose values or otherwise as instructed by the Investigator.

9.3.1.2 Non-Captured Expected Adverse Events

Non-Captured expected AEs may occur at any time in the normal course of managing diabetes. For the purpose of this study, they will be considered as non-captured expected AEs and will not be documented in the eCRF, these include:

- Asymptomatic hypoglycemia episode (see Section 9.2.1).
- Hyperglycemia without medical intervention.
- In the event of a sore finger, subjects will be advised to avoid taking self-monitoring blood glucose samples from that finger.
- In the event of a mild infection at a lancing site, the study subject will be reminded to wash hands before all blood tests and encouraged to consult their nurse or physician on the management of an infection.

Since these non-captured expected Adverse Events identified above are common as well as expected and pose minimal immediate risk to the subjects, they will not be tracked and logged as AEs during the course of the study. Investigators may log reports of these non-captured expected AEs as is customary within their practice.

These non-captured expected AEs will be handled as follows:

Subjects will be instructed to follow their personal physicians' instructions for management of low and high blood glucose values as well as for minor skin damage, minor bleeding and mild discomfort.

9.3.2 Unexpected Adverse Events

All AEs which do not meet the criteria mentioned under expected AEs (Section 9.3.1) are considered as unexpected AEs and will be documented in an AE Form in the eCRF.

9.4 Assessment of Causality in Relationship to Device

9.4.1 Related

An AE is deemed related with a device if **ALL** of the following criteria apply:

- There is a reasonable temporal sequence between AE and use of the device.
- It follows a known or expected response pattern of the device.
- It cannot be reasonably explained by the known characteristics of subject's clinical state.

Adverse events resulting from insufficiencies and/or inadequacies in the instructions for use or the deployment of the device will be classified as related.

Adverse events resulting from a user error will be classified as related.

9.4.2 Possibly Related

An AE is deemed possibly related if:

- There is a reasonable temporal relationship between the AE and use of the device; and
- It follows a known or expected response pattern of the device but could have been easily produced by a number of other aetiologies.

9.4.3 Unrelated

When there is no reasonable temporal association between the device and the AE or the event was related to the subject's clinical state or concomitant treatment(s).

9.4.4 Not Assessable

When there is not sufficient information to assess a relationship.

9.5 Period of Observation

All AEs ongoing at the time of study termination - irrespective their severity - should be followed up - via telephone - for a maximum of 5 days after the subject's last visit to the site. A medical statement should be included in the AE Form in the eCRF for all ongoing AEs after the Period of Observation.

9.6 Investigators' Responsibility to Report Serious Adverse Events

Investigators must immediately report all SAEs on the SAE Report Form which has been integrated in the eCRF - irrespective of expectedness or relationship to study procedures or study devices.

For reported deaths, the Investigator should provide any additional information, as requested and required, such as autopsy reports or terminal medical reports.

The Investigator should complete and (electronically) sign the form, and send it (electronically, within the eCRF system) to:

Study Safety Officer:	
-----------------------	--

In case, the eCRF system is not functioning, a paper version of the form should be completed by hand, signed and sent as described above (faxed or e-mailed).

If SAE/SADE information is unsatisfactory and essential data is missing, the Investigator is requested to conduct the necessary follow-up actions and/or to provide additional information as soon as possible.

9.7 Sponsor's Responsibility to Report Serious Adverse Events/Serious Adverse Device Effects

The below Stu	udy Safety Officer is responsi	ble for all safety	related topics of	the study:
Name:				
Email:				

Fax:

Phone:

Upon receipt of an SAE Report Form, the Study Safety Officer will:

- Review the SAE Report Form for completeness and make a medical assessment.
- Ensure that additional (initially, follow-up and final) information is obtained and communicated, as applicable.

After Safety Assessment the SAE is reported, as applicable, via the following internal lines: Roche Q-Function is responsible for reporting of initial, follow-up and final SAE reports to:

Regulatory Authorities.

Study Manager or designee is responsible for reporting to:

- Institutional Review Boards (IRB)
- Other Investigators.

10 Malfunction/Complaint Reporting Process

The FDA cleared medical device (ACCU-CHEK® Connect Diabetes Management System) observed in this study is used within the Intended Use. This is also valid for possible ACCU-CHEK® BG meters used by the Control group during the first 3 months of the study.

Accu-Chek® Customer Care - Call Center Cards

Roche Diabetes Care, Inc. will provide the Investigator, including the study site staff, with a template of the Accu-Chek® Call Center Card containing the Accu-Chek® Customer Care Service Center phone number, study name and Roche Diabetes Care, Inc. internal study number.

The study staff will distribute the Call Center Card when the Roche product is dispensed to study participants. Study subject(s) and parents/caregivers should be instructed to use this card when contacting the Accu-Chek[®] Customer Care Service Center to identify that they are participating in a Clinical Study using Roche products. The information requested by the Accu-Chek[®] Customer Care Service Center will enable Roche Diabetes Care, Inc. to meet its reporting obligations.

Subjects and parents/caregivers will be instructed to report any malfunctions/complaints to the Accu-Chek® Customer Care Service Center as described above, for the Roche product. Subjects may also have the option to report malfunctions/complaints to their Investigator during a study visit, whereby the Investigator and subject contact the Roche Diabetes Care, Inc. Accu-Chek® Customer Care Service Center together, to identify the subject is participating in a Clinical Study using Roche products. Contact details will be noted on subject's identification card.

10.1 Definitions

10.1.1 Definition of Malfunction

A "malfunction" is a failure of the device to meet its performance specifications or otherwise perform as intended. Performance specifications include all claims made in the labeling for the device.

10.1.2 Definition of Complaint

Complaint means any written, electronic or oral communication that alleges deficiencies related to the identity, quality, durability, reliability, safety, effectiveness or performance of a device after it is released for distribution. 21CFR 820.3(b)

11 Statistical Considerations and Data Analysis

The primary and secondary analysis as defined in this study protocol will be described in the Statistical Analysis Plan (SAP) and summarized in the final Clinical Study Report (CSR). All additional exploratory analyses required for publications or requested for different needs will be included in a separate Appendix e.g. Publication Analysis Plan (PAP). This might include any ad-hoc additional analyses not defined in the final version of the study protocol/amendment and the SAP.

11.1 Null Hypothesis and Sample Size Calculation

The primary outcome variable is change from baseline in PAID-C & T Parents at 6 months. A sample size of 75 patients per group will have 80% power (α =0.05, 2-sided) to detect a treatment effect size of 0.460. Given assumptions of common SD from 5-16, this sample size would be able to detect treatment group differences of 2.3 to 7.4, respectively. In order to account for possible drop-out prior to the 6 month endpoint, 100 subjects per group will be enrolled.

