2.1 Study Design Overview

This is a prospective, interventional, multi-center, post-market, 6-months, cluster randomized study, conducted in the US. In order to maintain a true control group for comparison, the investigational sites will be randomly assigned to one of the following treatments:

- Interventional Group ACCU-CHEK® Connect Diabetes Management System
- Control Group Usual care: Continued use of subjects' current diabetes devices

[figure not shown]

Figure 1 Study Design

Between 150 - 200 children with diabetes will be included in the clinical study and the duration of participation is 6 months for each subject. A cluster of 10-20 children is expected to enroll at each investigational site.

All subjects recruited by an Interventional Site will be provided with an ACCU-CHEK[®] Connect DMS (and up to one additional meter to keep at school), trained in the system's use, and asked to use this system for the following 6 months.

All subjects recruited by the Control site will continue to use their current diabetes management system.

All parents/caregivers independently of the age of their child are also part of the study, and will complete questionnaires about diabetes related stress, system use and other aspects of diabetes.

Furthermore, the health care providers (investigators and study staff) as well as school staff will also be asked to assess their preference in comparison to previously used systems. In order to obtain data prior to study start self-monitored blood glucose (SMBG) data from all subjects will be downloaded at Baseline using Diasend – for the data transfer to the eCRF

During the study the Control sites will continue to download data using Diasend whereas data download at Interventional sites will be managed by ACCU-CHEK® Connect DMS.

Control sites will continue to use data analysis methods according to their current practice for making therapy decision throughout the study. No change in behavior should be introduced by the study in this group and therefore they will not use data downloads via Diasend for therapy decisions, if this is not currently their practice, but they might need to perform downloads via Diasend for eCRF transfer only.

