The targeted study population is school-aged children, age 6-18 years, with type 1 diabetes currently managed by MDI therapy.

All parents/caregivers are also part of the study independently of the age of the child and will be asked to fill out questionnaires.

Recruitment will take place over three months at the site. Subjects will be recruited based on their own/their parents/caregivers' interest to participate in this study as well as verification of subject and parent eligibility through inclusion/exclusion criteria; see below.

Smartphones

The child/adolescent must currently be using a Smartphone with ability to download the ACCU-CHEK Connect System App accordingly OR able to use a Smartphone provided by the study sponsor exclusively for use in the study.

Specific device compatibility is determined via QR code on the AC Connect meter packaging. When scanned it either takes user to appropriate app-store (compatible device): Google play (Android) or Apple App Store (iOS) or to page that lists the compatible mobile devices.

Compatible phones and devices are continually changing: a compatibility list will be kept.

Number of subjects to be enrolled is between 150 and 200.

Health care providers (investigators and study staff) as well as school staff will also be asked to assess their preference in comparison to previously used systems.

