2.1.2 Sample size justification

Change from baseline in PAID-C & T parent, the primary endpoint was used to estimate the sample size requirement for the study. A sample size of 75 per group would be sufficient, with a power of 80% to detect a treatment effect of 0.460 with a significance level of 0.05. Given assumptions of SD of 5 to 16, the sample size would be able to detect treatment group differences of 2.3 (SD=5) to 7.4 (SD=16.0). 100 subjects per group will be enrolled to accommodate attrition.

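### The stated 80% power for an effect of 0.460 with 75 per group assumes independently randomised subjects; the cluster design and the permitted enrolment range do not deliver it

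*Protocol*

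**What the plan says.** Protocol 11.1 bases the sample size on the 6-month change in the parent PAID score: "A sample size of 75 patients per group will have 80% power" ("α =0.05, 2-sided") "to detect a treatment effect size of 0.460". It then translates this into points: "Given assumptions of common SD from 5-16, this sample size would be able to detect treatment group differences of 2.3 to 7.4, respectively". The Protocol synopsis carries the same figures, and SAP 2.1.2 repeats them: "A sample size of 75 per group would be sufficient, with a power of 80% to detect a treatment effect of 0.460". All three places raise enrolment to 100 per group, and each gives drop-out or attrition as the reason.

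The design sections describe a different kind of trial. Protocol 2.1 randomises investigational sites and adds: "A cluster of 10-20 children is expected to enroll at each investigational site". The Protocol synopsis and SAP 2.1.1 give 8 to 13 sites, and the SAP specifies 1:1 allocation. On total size, Protocol section 6 says: "Number of subjects to be enrolled is between 150 and 200". Protocol 6.4 rules out replacing drop-outs. None of the sample size passages mentions an ICC, a design effect or the number of clusters.

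**The concern.** When whole sites are randomised, families at one site share a clinic, its staff and its practice, so their outcomes tend to be correlated. The information in 75 families per group is then less than that of 75 independent families. A valid test also has to estimate between-site variation from only 8 to 13 sites. A calculation that ignores both overstates power and understates the detectable difference.

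The enrolment figures raise a second problem that does not depend on the ICC. If 100 per group are needed to finish with 75, a trial that may enrol 75 per group does not meet its own requirement.

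The figures concern the primary endpoint, and readers will use them to interpret the result. Someone who takes 80% power for 0.46 SD at face value could read a null result as stronger evidence against an effect of that size than the design can supply.

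**Working it through.** **Inputs from the documents.** n = 75 analysed per group, d = 0.460, two-sided α = 0.05, SD 5 to 16 (Protocol 11.1); 8 to 13 sites (synopsis, SAP 2.1.1); 10 to 20 children per site (Protocol 2.1); 150 to 200 enrolled in total (Protocol 6); 100 enrolled per group to leave 75 (Protocol 11.1), an implied loss of 1 − 75/100 = 25%. **Assumption:** ICC 0.01 to 0.05, because the documents give none.

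**Step 1: reproduce the plan's figure.** For independent subjects, power comes from the noncentral t distribution with noncentrality d × √(n/2) = 0.46 × √37.5 = 2.817 and 148 degrees of freedom (df). The result is 0.799. The effect detectable at 80% power is 0.4605. In points, 0.46 × 5 = 2.3 and 0.46 × 16 = 7.36. Every stated number is recovered with no cluster allowance, so none is hidden in it.

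**Step 2: add the clusters.** With k sites, the mean number analysed per site is m = 150/k. The design effect is DE = 1 + (m − 1) × ICC, and the effective size per group is 75/DE. Noncentrality becomes 0.46 × √(75/DE/2). Power is shown first with 148 df (design effect only) and then with k − 2 df. As in the plan's own calculation, no credit is taken for covariates.

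| Sites (m) | ICC | DE | Effective n per group | Power, DE only | Power, k − 2 df |
|---|---|---|---|---|---|
| 8 (18.75) | 0.01 | 1.177 | 63.7 | 73% | 59% |
| 8 | 0.02 | 1.355 | 55.4 | 67% | 53% |
| 8 | 0.05 | 1.888 | 39.7 | 53% | 41% |
| 10 (15) | 0.01 | 1.140 | 65.8 | 75% | 64% |
| 10 | 0.02 | 1.280 | 58.6 | 70% | 59% |
| 10 | 0.05 | 1.700 | 44.1 | 57% | 48% |
| 13 (11.54) | 0.01 | 1.105 | 67.8 | 76% | 69% |
| 13 | 0.02 | 1.211 | 61.9 | 72% | 65% |
| 13 | 0.05 | 1.527 | 49.1 | 62% | 55% |

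With ICC = 0, the k − 2 df alone take power to 65% (8 sites), 70% (10) and 73% (13).

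**Step 3: detectable effect at 80% power, ICC 0.02 to 0.05.**
- Design effect only: 0.4605 × √1.211 = 0.51 to 0.4605 × √1.888 = 0.63 SD.
- With k − 2 df: 0.55 SD (13 sites, ICC 0.02) to 0.76 SD (8 sites, ICC 0.05). That is 2.8–3.8 points at SD 5 and 8.9–12.1 points at SD 16, against the stated 2.3 and 7.4.

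**Step 4: the enrolment range.**
- 150 enrolled is 75 per group, and 75 × 0.75 = 56.25 analysed. Power for 0.460 is 68% with independent families. A 10% loss would give 76%. Only zero loss gives 80%.
- Eight sites of 10–20 children give 8 × 10 = 80 to 8 × 20 = 160, so 200 is out of reach at 8 sites with the expected cluster size. At 20 per site, 200 needs 200/20 = 10 sites.
- To analyse 75 per group at 8 sites after 25% loss, each site would have to enrol 18.75/0.75 = 25, above the expected 10–20. The 8-site rows above are therefore generous.

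The formulas assume equal cluster sizes and equal arms. Thirteen sites cannot be split exactly 1:1.

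**The case against.** The printed sum is correct for the formula used; what is missing is a design assumption. The size of the shortfall depends on choices the documents do not settle, and several of these favour the plan.

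- **ICC.** At 0.01, design-effect-only power is 73–76%, a modest loss.
- **Degrees of freedom.** Sites-minus-2 is a conservative choice. At 10 sites and ICC 0.02, about half of the fall from 80% to 59% comes from it.
- **Baseline adjustment.** The primary model in SAP 5.5.1 includes baseline PAID. If the baseline to follow-up correlation were 0.5, ANCOVA would cut the variance of the change score by the factor (1 + 0.5)/2 = 0.75. The effective n at 10 sites and ICC 0.02 would be 58.6/0.75 = 78.1, and power about 81% (71% with 8 df). The documents give no correlation and the stated calculation takes no such credit.
- **Full enrolment with no loss.** With 200 analysed and ICC 0.01, design-effect-only power is 83–86% (68–79% with sites-minus-2 df).
- **Enrolment.** No drop-out rate is stated, 10–20 per site is an expectation rather than a cap, and 10 or more sites can reach 200.

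These points stand as limits on how large the shortfall is. None of them restores the stated claim, which is 80% with 75 analysed per group and no covariate credit.

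A further argument is that the planned ANCOVA and t-test carry no site term, so the powers above belong to a different test. Under the same assumptions the planned test would reject about 76–78% of the time at ICC 0.02 and 73–75% at ICC 0.05. That is bought with error. With 15 per site, the true two-sided level is 2 × (1 − Φ(1.96/√DE)), which is 6.6% at ICC 0.01 and 13% at ICC 0.05. Power of 80% at a true 5% level is not delivered by either test.

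**Conclusion.** The concern holds. The stated power and detectable differences are those of an individually randomised trial. With 75 analysed per group and no covariate credit, any positive ICC puts power at a true 5% level below 80%.

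The omission itself is certain from the documents; its size rests on an assumed ICC. The figures for 0.02 to 0.05 are in Steps 2 and 3. An ICC near 0.01, useful baseline adjustment or near-complete follow-up of 200 families would narrow the gap.

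The inconsistency between 100 per group and a permitted total of 150 stands without any ICC. The 68% there rests only on the 25% loss implied by the plan's own step from 100 to 75.

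**What to change.** Revise Protocol 11.1, the Protocol synopsis and SAP 2.1.2 together:

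1. State that sites are the unit of randomisation. Give the number of sites, the mean number analysed per site and the assumed ICC range with its basis.
2. Replace the single power statement with power for 0.460 and the detectable difference under the cluster design, for example as in the table above. Name the analysis and degrees of freedom to which the figures refer. If credit is taken for baseline adjustment, state the assumed correlation.
3. State the assumed drop-out rate. Either give the power at the lower enrolment limit of 150 or make the range agree with 100 per group.
4. Check that the number of sites multiplied by the expected cluster size reaches the stated total.

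The cost is text only. No additional patients, visits or procedures are asked for. The stated power and detectable difference become less favourable.

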11.2 Populations for Analysis

The intent-to-treat (ITT) population will consist of all families that have completed at least one questionnaire at both baseline and end of study.

The full analysis set (FAS) will consist of all families that have completed the parent/caregiver PAID-PR questionnaire at both baseline and end of study.

The safety population will consist of all subjects.

11.3 Subject Demographics and Baseline Characteristics

Child/Adolescent with diabetes

- Demographics (age/gender/race/ethnicity)
- Collect and record most recent HbA1c including date of measurement.
- Obtain and record Diabetes Background and History including insulin therapy, previous personal CGM, SMBG habits and frequency and diabetes complications
- Obtain and record Diabetes Medication including but not limited to brand name(s) of insulin
 used, total daily dose, total basal and bolus doses, sensitivity factors, etc.
- Identify Diabetes Management responsibility (parent/caregiver primarily managing, child selfmanaging, or child currently transitioning to self-management
- Communication regarding diabetes parents/caregiver when at school
 - Method: (phone/email/text)
 - Frequency: (multiple times/day, daily, weekly, as needed for problem resolution only).
- Number of missed school days in past 3 months (diabetes-related)

Parent / caregiver

- Demographics (age/gender/race/ethnicity/education/job- and marital status)
- Communication regarding diabetes with school staff
 - o Method: (phone/email)
 - o Primary Contact: (school nurse, teacher, or other school staff)
 - Frequency: (Multiple times/day, daily, weekly, as needed for problem resolution only)
- Number of missed work days in past 3 months (diabetes-related)

All subject characteristic variables will be summarized descriptively. Continuous variables will be summarized in terms of descriptive statistics including the number of subjects (N) without missing values, mean, standard deviation (SD), and range

Categorical variables will be summarized in terms of absolute frequencies and percentages. In general, the denominator for the percentage calculation will be based upon the total number of subjects in the study population, unless otherwise specified.

